## 10 STATISTICAL CONSIDERATIONS

### 10.1 OBJECTIVES AND ENDPOINTS

OBJECTIVES	ENDPOINTS	JUSTIFICATION FOR ENDPOINTS
Primary		
Phase I: To determine the recommended phase 2 dose (RP2D) of KPT-8602 in combination with Inqovi in adult participants with higher-MDS	- Recommended phase 2 dose (RP2D), as determined by the number of participants with DLTs reported at each dose level studied (Section 3.1.1 ) -Any toxicities identified from Day 1 of study drug through 28 days after the first dose. AEs are reported by type and grade. -ORR (defined as CR+PR+mCR with HI) per each cohort Responses will be assessed after every cycle with CBC and at the end of Cycles 2 and 6 with bone marrow assessment during treatment and every 3-6 months after that until time of disease relapse, disease progression, or death, or 8 years, whichever occurs first.	Standard endpoint for Phase I protocol Efficacy evaluation, standard for Phase II protocol
Secondary		
Phase I: To characterize the PK properties of KPT-8602 in combination with Inqovi in MDS participants	-AUC, half-life, and steady state concentration, measured by the KPT-8602 blood concentration 1, 2, 3, 4, 8, 24 and 48 hours after the product administration on days 8 and 21 of cycle one	PK studies to evaluate for adequate absorption of therapy and further define half-life/AUC and other properties of the study drug, when given in combination with Inqovi
Phase II: To further evaluate the PK properties and safety of KPT-8602 in combination with Inqovi in MDS participants	-Safety, as measured by: Incidence of AEs, SAEs; and AEs leading to discontinuation, death, and laboratory abnormalities, assessed at least weekly through cycle 3 and then at the start and every cycle after that	Confirm safety of the study drug at the RP2D
Exploratory		
To evaluate the relationship between KPT-8602 exposure (PK) and response	Each of these will be evaluated using descriptive methods and reported as exploratory results. If any statistical	Evaluate mechanism of the study drug, target engagement,

OBJECTIVES	ENDPOINTS	JUSTIFICATION FOR ENDPOINTS
To evaluate changes in XPO1 mRNA expression and other potential PD markers with treatment	tests are performed in these analyses, the results will be presented without adjustment for multiple comparisons but reported in the context of the number of tests performed. See Section 5 for collection timepoints.	relationship between exposures and response, and treatment impact on quality of life.
To assess changes in DNA damage repair by evaluation of gammaH2AX levels		
To evaluate compliance and feasibility of administering PRO in this patient population		
To evaluate tolerability of treatment by assessing symptomatic adverse events, physical function and side effect bother		
To longitudinally describe and evaluate disease and treatment-related symptom severity and functional well-being		
To determine meaningful change in disease and treatment related symptoms and functional well-being by using anchors		
To evaluate changes in DNA methylation status pre- and post-treatment		
To evaluate changes in cell composition in the bone marrow and peripheral blood microenvironment pre- and post-treatment		
To evaluate changes in genetic clonal diversity during treatment		
To evaluate changes in gene expression patterns of tumor suppressor genes and oncogenes (including DNMT3B expression)		
To evaluate the influence of splicing factor mutations (U2AF1, SRSF2, SF3B1, ZRSR2) on nuclear shuttling		
To evaluate the degree of disruption of ribosome biogenesis after XPO1 inhibition		
To evaluate changes in nuclear and cytoplasmic protein composition by mass spectrometry		

OBJECTIVES	ENDPOINTS	JUSTIFICATION FOR ENDPOINTS
To evaluate other clinical outcomes	-Secondary clinical outcomes, including: overall improvement rate (OIR), transfusion-independence (TI), cytogenetic response rate, time to best response (CR, PR, marrow CR + HI, HI), DFS, PFS, LFS, and OS; assessed every 3-6 months	Common set of outcomes reported in MDS therapy studies

## 10.2 STATISTICAL HYPOTHESIS AND SAMPLE SIZE DETERMINATION

The trial will begin with a phase I dose-escalation phase using a standard 3+3 design which will enroll participants with relapsed/refractory HR-MDS. Up to 18 participants may be enrolled based on the 3+3 design.

Participants will be eligible for the DLT evaluation if  $\geq 90\%$  (9 out of 10 doses) of KPT-8602 and  $\geq 80\%$  (4 out of 5 doses) of Inqovi were taken within the DLT period. Participants not evaluable for toxicity, will be replaced in the dose level.

Phase II will use a Simon's minimal two-stage design, applied separately as noted below:

- Trial will be conducted using a Simon minimax two-stage phase II trial design to rule out an unacceptably low response rate of 25% ( $p_0=0.25$ ) in favor of an improved response rate of 45% ( $p_1=0.45$ ) in order to determine if the combination of KPT-8602 with Inqovi will be able to improve upon an expected 30-40% response rate in participants who have received other agents. With two-sided alpha=0.05 and beta=0.20, the first stage will enroll 21 evaluable participants, and if 0 to 5 of the 21 have a response, then no further participants will be accrued. If 6 or more of the first 21 participants have a response, then accrual would continue until a total of 43 evaluable participants have been treated. If there are only 6-16 participants with a response out of 43 participants, this would be an uninterestingly low response rate. If there were 17 or more of 43 (39.5%) who experienced a response, treatment would be sufficiently interesting to warrant further study in later trials. The probability of early termination under the null (25%) response rate is 56.7%.

It is expected that up to 12-15 participants with MDS may be accrued per year. Thus, in order to accrue up to  $18 + 43 = 61$  participants (which may be reduced by up to 6 if up to 6 participants in phase I may be included in phase II), and to allow for a small number of inevaluable participants (12), it is expected that 3-4 years may be required to accrue the required 73 participants. Note: To allow for screen failures (7), the accrual ceiling will be set at 80 participants for the purposes of the NIH accrual ceiling.

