**Design:**

- Participants with HR-MDS will be enrolled in both Phase I and II.
- Participants will be treated with Inqovi at a fixed dose of 1 tablet (35 mg decitabine and 100 mg cedazuridine) daily on Days 1-5 of each 28-day cycle, followed by KPT-8602 at escalating doses (Phase I) or the RP2D (Phase II).
- In Phase I, KPT-8602 will be dose-escalated following a standard 3+3 design, with a starting dose level of 10 mg for 10 days (staggered) within a cycle. If tolerated, the dose will be escalated to 14 days per cycle, or dose de-escalated to 5 mg at 14 or 10 days.
- This study will be done at the NIH Clinical Center with an enrollment of up to 80 planned participants.

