### 3.1.2 Dose Escalation

In a phase I/II study (NCT 02649790) that evaluated single agent eltanexor in higher-risk MDS, 2 doses were evaluated: 5 patients received 10 mg and 15 patients received 20 mg, every day for 5 days per week of a 28-day cycle. The majority of patients were aged  $\geq 75$  and all were treated and refractory to hypomethylating agents. None of the patients experienced dose-limiting toxicities (DLTs) and the RP2D for eltanexor was selected as 10 mg given on days 1-5 of each week of a 28-day cycle in HR-MDS (20/28 days). Given the overlap in toxicities, particularly hematologic, between hypomethylating agents and eltanexor, our starting dose was set at 10 mg PO daily on Days 8-12 and Days 15-19 (total of 10 days per 28-day cycle as opposed to 20 days per 28-day cycle in NCT 02649790).

In Phase I, dose escalation will proceed in cohorts of 3-6 participants. The MTD is the dose level at which no more than 1 of up to 6 participants experience DLT during the first cycle (28 days) of treatment, and the dose below that at which at least 2 (of  $\leq 6$ ) participants have DLT as a result of the drug.

Participants in Cohort 1 will be eligible for the DLT evaluation if  $\geq 90\%$  (9 out of 10 doses) of KPT-8602 and  $\geq 80\%$  (4 out of 5 doses) of Inqovi were taken within the DLT period. Participants not evaluable for toxicity, will be replaced in the dose level.

Dose Escalation Schedule	
Dose Level	Dose of KPT-8602
Level -2	5 mg PO daily on Days 8-12 and Days 15-19
Level -1	5 mg PO daily on Days 8-21
Level 1 (starting dose)	10 mg PO daily on Days 8-12 and Days 15-19
Level 2	10 mg PO daily on Days 8-21

Dose escalation will start at dose level 1 and follow the rules outlined in the Table below.

Number of Participants with DLT at a Given Dose Level	Escalation Decision Rule
0 out of 3	Enter up to 3 participants at the next dose level
$\geq 2$	Dose escalation will be stopped. This dose level will be declared the maximally administered dose (highest dose administered). Up to three (3) additional participants will be entered at the next lowest dose level if only 3 participants were treated previously at that dose.

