### 3.1.3 Dose Expansion

If no DLTs are observed at the highest planned dose level for evaluation (dose level 2), dose escalation will stop and this will be considered the recommended phase 2 dose (RP2D) of KPT-8602. Phase II may begin once the RP2D has been identified.

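### The Phase I maximum of 18 does not follow from the four-level 3+3 rules, which allow up to 24; the accrual sum is then 86, or exactly 80 if six Phase I participants count in Phase II

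*Combined protocol and SAP*

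**What the plan says.** Section 10.2 gives the Phase I maximum: "Up to 18 participants may be enrolled based on the 3+3 design". It adds the Phase II maximum of 43 evaluable participants to reach 61, then 12 inevaluable participants to reach 73. After 7 screen failures, "the accrual ceiling will be set at 80 participants". It also remarks that the 61 could fall by up to 6 if up to 6 Phase I participants are included in Phase II. The sum to 80 does not use that reduction.

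The escalation rules are in Section 3.1.2:
- Four levels are listed: -2, -1, 1 and 2. "Dose escalation will start at dose level 1 and follow the rules outlined in the Table below".
- Level size: "In Phase I, dose escalation will proceed in cohorts of 3-6 participants".
- After 0 of 3 with a DLT: "Enter up to 3 participants at the next dose level".
- After a level fails: "Up to three (3) additional participants will be entered at the next lowest dose level", on condition that only 3 were treated there before.
- At least 6 participants must be entered at the RP2D.

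The précis (Design) describes movement both ways from the start: "If tolerated, the dose will be escalated to 14 days per cycle, or dose de-escalated to 5 mg at 14 or 10 days". Section 3.1.3 sets the top of the range: "If no DLTs are observed at the highest planned dose level for evaluation (dose level 2), dose escalation will stop".

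**The concern.** Eighteen is 3 x 6, but four levels can be visited. The rules open the next level while the current one holds only 3, and send participants back to that lower level if the higher one fails. Level 1 can therefore pass at first, level 2 fail, level 1 fail on its second group of 3, and both lower levels still be needed.

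The figure is presented as a design maximum, and 61, 73 and 80 all inherit it. If it is too low, the ceiling has less room than the plan suggests, and on the longest path completing Phase II depends on an overlap that the plan mentions but does not settle. Neither the dose-finding rule nor the Phase II operating characteristics are at stake.

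**Working it through.** **1. The plan's own sum.** 18 + 43 = 61; 61 + 12 = 73; 73 + 7 = 80. It reproduces exactly.

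**2. Where 18 comes from.** Start at level 1 and never open level 2. Level 1 fills to 6 and fails, level -1 fills to 6 and fails, level -2 fills to 6: 3 x 6 = 18. So 18 is the maximum if level 2 is never opened.

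**3. Maximum over all paths.** Inputs from Section 3.1.2: start at level 1; groups of 3, at most 6 per level; 2 or more DLTs fails a level; after failure, go to the level below and add 3 if it holds only 3; at least 6 at the RP2D. One assumption is added from the précis: an untested lower level may be opened. Inevaluable participants are assumed to be covered by the 12. A longest path is:

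| Step | Level | Outcome | Treated at that level |
|---|---|---|---|
| 1 | 1 | 0/3, escalate | 3 |
| 2 | 2 | expands, 2 or more DLTs, fails | 6 |
| 3 | 1 | 3 more, 2 or more DLTs, fails | 6 |
| 4 | -1 | expands, 2 or more DLTs, fails | 6 |
| 5 | -2 | expands | 6 |

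Total 6 + 6 + 6 + 6 = 24. Full enumeration of paths confirms 24 as the maximum. By final dose, the maximum is 12 if the RP2D is level 2 or level 1, 18 if it is level -1, and 24 if it is level -2 or if no dose qualifies.

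**4. The decision table read strictly.** The table adds participants at a lower level only where 3 were treated before. It has no row for opening an untested lower level. On that reading only levels 1 and 2 are used: 6 + 6 = 12. Neither reading gives 18.

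**5. The sum carried through.**

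| Phase I | Overlap with Phase II | + 43 | + 12 | + 7 |
|---|---|---|---|---|
| 18 | none (the plan) | 61 | 73 | 80 |
| 24 | none | 67 | 79 | 86 |
| 24 | 6 | 24 + 43 - 6 = 61 | 73 | 80 |

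Phase I sizes above 18 can only be 21 or 24. Every such path ends either with no RP2D, so no Phase II, or with level -2 as RP2D and exactly 6 treated there. Six participants are therefore available for the overlap whenever it matters.

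**6. How likely it is.** The documents give no DLT rates for the combination, so these are assumptions. Probabilities are exact, from the enumeration.

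| DLT rate, levels -2, -1, 1, 2 | P(Phase I > 18) | P(Phase I = 24) |
|---|---|---|
| 15% at all | 0.17% | 0.09% |
| 20% at all | 0.55% | 0.28% |
| 30% at all | 1.89% | 0.77% |
| 40% at all | 2.75% | 0.85% |
| 50% at all | 2.17% | 0.48% |
| 5, 10, 20, 35% | 0.37% | 0.18% |
| 15, 25, 35, 50% | 2.51% | 0.88% |

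Mean Phase I size is between 10.5 and 12.9 in these scenarios. The chance that 24 are treated and an RP2D is still found, the only 24-participant case that touches the Phase II sum, is 0.08% to 0.73%.

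**The case against.** The strongest reply is that the ceiling already holds. A reader who stops at 86 might infer that the plan breaches its own accrual limit. The documents do not support that: Section 10.2 allows up to six Phase I participants to count in Phase II, six at the RP2D always exist when a long Phase I is followed by Phase II, and the sum is then exactly 80. A shortfall would also need Phase II to pass its first stage, all 12 inevaluable and all 7 screen-failure places to be used, and the overlap not to be applied.

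That reply stands against the claim of a breach. It does not rescue the 18, which is a statement about Phase I alone. The overlap is also worded as a possibility, the plan's sum leaves it out, and no rule says when a Phase I participant counts. The study calendar requires marrow at the end of Cycles 2 and 6 for Phase II, with other times as clinically indicated, and places a Phase I marrow at Cycle 1 Day 28. Section 10.1 assesses response with marrow at the end of Cycles 2 and 6. Phase I participants may therefore lack the assessments that the Phase II endpoint uses.

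A second reply is that 24 is not in the rules as written, because the decision table never describes entry to an untested lower level. This is right as far as it goes: 24 rests on reading the table with the précis and the listed levels -1 and -2. De-escalation is plainly intended, since Section 3.1.2 also refers to de-escalation decisions, and the strict alternative gives 12.

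**Conclusion.** The stated Phase I maximum of 18 is wrong for the design described. The maximum is 24 if de-escalation to both lower levels is allowed, and 12 if the decision table is read strictly. Eighteen holds as a maximum if level 2 never opens, a limit no section states.

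The effect on the accrual sum is 86 against 80 without the overlap, an excess of 6, and exactly 80 with it. It would be wrong to conclude that the ceiling is necessarily exceeded. What can be said is that it has no slack on the longest path, and that it holds there only if the overlap is applied.

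The practical size is small: more than 18 in 0.17% to 2.75% of trials, and 24 in under 1%, under the assumed DLT rates. Power, error rates and expected enrolment are unaffected. This is worth correcting because it is a stated maximum that feeds the accrual ceiling, but it is a minor point.

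**What to change.** In Section 10.2, restate the Phase I maximum as 24, or reconcile the 18 with the dose levels and escalation rules in Section 3.1.2 and the précis. The missing description of entry to an untested lower level should be reconciled with the précis at the same time.

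State whether the six participants at the RP2D count toward the 43 and, if so, on which response assessments. Then restate the accrual sum on that basis: 67, 79 and 86 without the overlap, or 61, 73 and 80 with it.

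The cost is a restated figure and a clarifying sentence or two, with no change in expected enrolment. The ceiling itself needs to change only if the overlap is ruled out.

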## **1 INTRODUCTION**

### **1.1 STUDY OBJECTIVES**

#### **1.1.1 Primary Objective**

- Phase I: To determine the recommended phase 2 dose (RP2D) of KPT-8602 in combination with Inqovi in adult participants with higher-risk MDS
- Phase II: To determine the overall response rate (ORR) of KPT-8602 in combination with Inqovi in adult participants with higher-risk MDS

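### Section 10.2: passing the 25%-versus-45% rule does not show improvement on the expected 30-40% response rate, and 73 participants at 12-15 per year need about 5-6 years, not 3-4

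*Combined protocol and SAP*

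**What the plan says.** Section 10.2 sets up Phase II as a Simon minimax two-stage design "to rule out an unacceptably low response rate of 25" per cent, in favour of 45%, with two-sided alpha 0.05 and beta 0.20. Accrual stops if 5 or fewer of the first 21 evaluable participants respond. Otherwise it continues to 43, and the section concludes: "If there were 17 or more of 43 (39.5%) who experienced a response, treatment would be sufficiently interesting" enough for later trials. The stated purpose of this test is to find out whether the combination can "improve upon an expected 30-40% response rate in participants who have received other agents".

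Section 1.1.1 gives a plainer Phase II objective: "To determine the overall response rate (ORR) of KPT-8602 in combination with Inqovi". Section 10.1 specifies the endpoint as "ORR (defined as CR+PR+mCR with HI) per each cohort". Section 10.4.2 plans to report the response fraction with a 95% confidence interval.

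On timing, section 10.2 states: "It is expected that up to 12-15 participants with MDS may be accrued per year". It adds 18 Phase I and 43 Phase II participants to get 61, a total "which may be reduced by up to 6 if up to 6 participants in phase I may be included in phase II". It then allows for 12 inevaluable participants and concludes that "it is expected that 3-4 years may be required to accrue the required 73 participants".

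**The concern.** Two statements in section 10.2 do not follow from the numbers beside them.

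The first is the purpose clause. A single-arm test against 25% controls error at 25%. It says nothing with controlled error about a benchmark of 30-40%, and here the smallest successful result falls within that benchmark. If the clause stays, 17 of 43 could be presented as an improvement on what other agents achieve, which the rule cannot support. The 30-40% range appears nowhere else in the document as a response-rate benchmark, and it comes with neither a source nor an endpoint definition.

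The second is the accrual time. Three to four years at the stated rate does not produce 73 participants. The trial runs at one centre (Précis, Design), so an understated duration bears on feasibility and resources. No stopping rule depends on it.

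**Working it through.** **Inputs (all section 10.2).** p0 = 0.25; p1 = 0.45; two-sided alpha 0.05, taken as 0.025 one-sided; beta 0.20; n1 = 21, stop at 5 or fewer; n = 43, success at 17 or more; benchmark 30-40%; accrual up to 12-15 per year; 73 participants; overlap up to 6; stated duration 3-4 years.

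**Step 1: reproduce the design.** With X1 ~ Bin(21, p) and X2 ~ Bin(22, p),

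P(success | p) = sum over x = 6 to 21 of P(X1 = x) × P(X2 ≥ 17 − x).

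An exact search for the minimax design at one-sided 0.025 and 80% power returns 5/21 and 16/43, as in the plan.

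- Type I error at p = 0.25: 0.0245
- Power at p = 0.45: 0.8005
- Early termination at p = 0.25: P(X1 ≤ 5) = 0.5666, against the stated 56.7%

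The design is right for the hypotheses it names.

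**Step 2: apply the rule to the 30-40% range.** This assumes that the benchmark is on the trial's ORR scale.

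| True response rate | Probability of passing |
|---|---|
| 25% | 2.45% |
| 30% | 11.4% |
| 35% | 31.1% |
| 40% | 57.3% |
| 45% | 80.0% |

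A regimen at the top of the benchmark, and so no better than it, passes more often than not.

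**Step 3: what the interval would show.** Section 10.4.2 names no interval method. The table uses exact (Clopper-Pearson) fixed-sample 95% intervals. They are descriptive and are not proposed thresholds.

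| Responses of 43 | Observed | Exact 95% CI |
|---|---|---|
| 17 | 39.5% | 24.98%-55.6% |
| 19 | 44.2% | 29.1%-60.1% |
| 20 | 46.5% | 31.2%-62.3% |
| 24 | 55.8% | 39.9%-70.9% |
| 25 | 58.1% | 42.1%-73.0% |

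The interval still contains 30% at 17-19 responses and still contains 40% at 17-24.

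At 17/43 the lower limit falls just below 25% although the two-stage test rejects 25%. The single-stage tail P(X ≥ 17 | 43, 0.25) is 0.0252, while the two-stage probability is 0.0245. The Wilson lower limit is 26.4%.

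**Step 4: accrual.** Years = participants ÷ annual rate.

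| Total | How it arises | At 15 per year | At 12 per year |
|---|---|---|---|
| 73 | 61 + 12, as stated | 4.9 | 6.1 |
| 67 | 73 − 6 overlap | 4.5 | 5.6 |
| 61 | 18 + 43, none inevaluable | 4.1 | 5.1 |
| 55 | 61 − 6, none inevaluable | 3.7 | 4.6 |
| 51 | 18 + 21 (stop after stage 1) + 12 | 3.4 | 4.3 |

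In the other direction, 3 × 12 = 36 and 4 × 15 = 60, so 3-4 years yields 36-60 participants. Reaching 73 needs 73/4 = 18.3 to 73/3 = 24.3 per year. Because the rate is given as an upper figure, 4.9-6.1 years is a minimum.

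**The case against.** On the first point, the operative text is coherent. It rules out 25%, and it attaches only a recommendation for further study to 17 of 43. The 30-40% figure can be read as motivation for setting p1 at 45%, above the whole range. The analysis sections promise only a response fraction with an interval, and an interval of about 25-56% would itself show that 30-40% had not been excluded. Section 1.2.2 also gives some context: 40% CR plus marrow CR with another combination in relapsed or refractory disease, and a response in fewer than half of patients on HMAs.

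Much of this stands. The rule, the error rates and the planned interval are sound, and a misleading claim is a risk rather than a certainty. It does not rescue the clause, which makes the comparison the purpose of the test. Placing p1 above the range governs power; rejecting 25% does not establish 45%. The figures in section 1.2.2 are not on this trial's ORR definition.

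On the second point, 73 is built from maxima. A clean escalation could need only 9 participants in Phase I (3 at level 1 and 6 at level 2). With full overlap that gives 9 + 43 − 6 = 46, or 3.1-3.8 years. Adding the 12 inevaluable gives 58, or 3.9-4.8 years. So 3-4 years is attainable on a favourable path, but the sentence gives that duration for 73.

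**Conclusion.** Both points hold. The two-stage design is correct for 25% versus 45%, but meeting it does not show improvement over 30-40%. The minimum success lies inside that range, and true rates of 30%, 35% and 40% pass with probability 11.4%, 31.1% and 57.3%. Those probabilities assume that the benchmark uses the trial's ORR definition, which the plan does not say. That 25% lies below the range and 39.5% inside it needs no calculation.

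The accrual time for 73 is understated by about 1-3 years (4.87 − 4 = 0.87 to 6.08 − 3 = 3.08). Counting six Phase I participants in Phase II does not close the gap. Neither point touches the sample size, the stopping boundaries or the error rates. The first affects how a positive result may be described, and the second affects feasibility planning.

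**What to change.** Keep the design and the decision rule. For the purpose clause, do one of the following:

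- **Delete it**, and justify 25% as the reference rate for this HMA-failure population.
- **Keep it** with its source and endpoint definition, and add a sentence such as: *17 or more responses in 43 meets the two-stage criterion against 25% and warrants further study; it does not by itself show improvement over 30-40%.*

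Wherever the result against 25% is described, say that it rests on the two-stage test, because the fixed-sample exact interval at 17/43 starts at 24.98%.

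For accrual, either restate full accrual of 73 as about 5-6 years at the stated rate, or correct the rate; 3-4 years needs about 18-24 per year.

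The cost is wording only. The downside is a more modest stated claim and a longer stated timeline.
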